4.2. Randomization, Stratification, and Blinding

Approximately 156 eligible subjects will be randomly assigned to one of the following 3 treatment groups in a 1:1:1 ratio:

- Approximately 52 subjects are assigned to GR-MD-02 in dose of 2 mg/kg LBM
- Approximately 52 subjects are assigned to GR-MD-02 in dose of 8 mg/kg LBM
- Approximately 52 subjects are assigned to placebo

The randomization mechanism for the study will be deployed within an interactive web response system (IWRS). Unblinded biostatisticians will generate the randomization schedule using SAS software Version 9.2 or later for IWRS which will link sequential subject randomization numbers to treatment codes allocated at random with a 1:1:1 randomization ratio.

Except in an emergency, investigators, Galectin, or other persons involved in study conduct will not know the randomization schedule and study drug allocation before study completion. The IWRS system will be used if emergency unblinding is required. This would generally only be used in an emergency, when knowledge of the actual treatment becomes medically necessary.

4.3. Analysis Set

4.3.1. Full-Analysis Set

The full-analysis set (FAS), or intent-to-treat group, will consist of all subjects who were randomly assigned to IMP. The FAS will be used as the primary efficacy analysis set.

All subjects in the FAS set will be analyzed according to the treatment they were randomized to receive.

4.3.2. Modified-Intent-to-Treat Set

The Modified-Intent-to-Treat (MITT) set will consist of all subjects who were randomly assigned, received at least 1 infusion, and had at least 1 post-baseline efficacy assessment.

All subjects in the MITT set will be analyzed according to the treatment they were randomized to receive.

4.3.3. Per Protocol Set

The per protocol (PP) set will consist of all FAS subjects who have at least 80% compliance with study treatment, have not taken any prohibited medication, have no significant protocol deviations, and restricted to each subject's time on IMP plus 30 days thereafter for the analysis of progression of efficacy events.

All subjects in the PP set will be analyzed according to the treatment they actually received.

4.3.4. Safety Set

The safety set will consist of all subjects who received any IMP. All subjects in the safety set will be analyzed according to the treatment they actually received.

4.3.5. Pharmacokinetic Set

The PK analysis set will consist of subjects who provide at least 1 C_{max} PK sample.

5. Subject Disposition

5.1. Disposition

A disposition of subjects includes the number and percentage of subjects for the following categories: subjects who were randomized, subjects who completed the study, subjects who discontinued from the study. All percentages will be based on the number of subjects randomized using the FAS population.

The reasons for discontinuation of study participation will also be summarized in the tables.

Subject disposition data will be presented in a listing.

5.2. Protocol Deviations

Protocol deviations/violations will be identified and assessed by the investigator in accordance with the procedures or processes approved by the sponsor. The protocol deviations/violations will be defined prior to unblinding of the database. The significant protocol deviations/violations will be summarized by treatment group using the FAS population. A listing of subjects with all protocol deviations/violations will also be provided.

6. Demographics and Baseline Characteristics

This summarization will be based on the FAS population set and presented by treatment group and overall. Descriptive statistics will be calculated for continuous variables and frequency counts and percentages will be applied to categorical variables. No inferential statistics will be presented. All subject demographic and baseline characteristic data will be presented in listings.

6.1. Demographics

The demographics and baseline characteristics summary will be presented in a table by treatment group and overall. The following variables will be included:

- Age (years)
- Sex (male, female)
- Race

- Ethnicity
- Baseline height (cm)
- Baseline weight (kg)
- Baseline body mass index (BMI) (kg/m²)
- Baseline lean body mass (LBM) (kg)
- Baseline Alcohol Use Disorders Identification Test (AUDIT)

Age in years will be calculated by using the date of birth from the informed consent date and will be rounded down to an integer. BMI is calculated as follows:

$$\text{BMI} = \text{weight (kg)} / (\text{height (m)})^2$$

Alcohol consumption will be evaluated by AUDIT which contains 10 questions scaling from 0 to 4, the total score based on the sum of 10 individual scores will be summarized.

6.2. Baseline Disease Characteristics

Summaries of baseline disease characteristics will be presented by treatment group and overall, and include, but are not limit to the baseline HVPG, diagnosis of NASH, CPA, FibroScan[®] (if available) score, Ishak histopathological stage and Brunt-Kleiner histopathological stage.

6.3. Alcohol Usage

Alcohol timeline followback (TLFB) will be used to assess subjects' alcohol consumption for the years 2015, 2016 and 2017. Subjects' daily drinking will be recorded as amount of standard drink on the calendar. The estimate daily drinking over the time will be summarized by treatment group and overall for the FAS population.

6.4. Medical and Surgical History

The number and percentage of subjects with any medical and surgical history will be summarized overall and for each body system. Body systems will be included as recorded on the eCRF. Percentages will be calculated based on number of subjects for the safety population.

Subject medical history data including specific details will be presented in a listing.

6.5. Inclusion and Exclusion Criteria

Subjects who do not meet all inclusion and exclusion criteria, as presented in Section 4.1.1 and 4.1.2 of the protocol, will be presented in a listing.

7. Treatments and Medications

This summarization of treatments and medications will be based on the safety population set and presented by treatment group and overall. Descriptive statistics will be calculated

for continuous variables and frequency counts and percentages will be applied to categorical variables. No inferential statistics will be presented.

7.1. Prior and Concomitant Medications

All prior medications for liver cirrhosis and NASH will be recorded in the eCRF and all other medications taken from 30 days prior to screening and throughout the entire duration of the subject's participation in the study will be documented in the eCRF. A concomitant medication is defined as medications taken any time after the first infusion of IMP. A prior medication is defined as nonstudy medications discontinued prior to the first infusion of IMP.

Missing start dates for concomitant medications data will be handled as follows (where UK, UKN and UKNW indicate unknown or missing Day, Month and Year respectively):

- UK-MMM-YYYY: impute 01-MMM-YYYY. If the month and year are the same as the first dose month and year, then impute the date of the first dose;
- UK-UKN-YYYY: If the year is prior to the year of the first dose, impute 01-JAN-YYYY of the collected year. If the year is the same as the first dose year, then impute the date of the first dose. If the year is after the year of the first dose, impute 01-JAN-YYYY;
- UK-UKN-UKNW: impute date of the first dose.

Missing stop dates for concomitant medications data will be handled as follows (where UK, UKN and UKNW indicate unknown or missing Day, Month and Year respectively):

- UK-MMM-YYYY: impute the last day of the month;
- UK-UKN-YYYY: impute 31-DEC-YYYY;
- UK-UKN-UKNW: leave as missing.

If imputed start date is after the end date of concomitant medication, the start date will be set same as end date.

Prior and concomitant medications will be coded using the World Health Organization Drug dictionary (WHO Drug) Version 1 March 2015. The dictionary will be updated throughout the life of the project to allow for the most recent version of the dictionary to be used. The medication names will be coded according to the Anatomical Therapeutic Chemical (ATC) class and preferred terms provided in the dictionary.

Prior and concomitant medications will be summarized in separate tables. The tables will present the number and percentage of subjects by ATC class and preferred term for each treatment group and overall. ATC classes will be sorted in decreasing order of frequency based on the total number of subjects who take each medication in the total column, while preferred terms within each drug class will be presented alphabetically. In addition, the total number of medications and the number and percentage of subjects receiving at least 1

medication will also be presented. If a subject has multiple medications for a given preferred term the subject will only be counted once.

All prior and concomitant medications will be presented in a listing.

7.2. Study Treatments

GR-MD-02 and matching placebo will be available in 10-mL sterile vials at a concentration of 30 mg/mL. The treatment regimen consists of 26 injection visits biweekly from week 1. The dosing will be determined by LBM, since it is anticipated that many subjects will be obese and GR-MD-02 is distributed primarily in the blood compartment.

7.2.1. Extent of Exposure

Duration of exposure is defined as the total number of days a subject is exposed to study medication and will be presented as the total number of days from the first infusion date to the last infusion date (date of last infusion minus the date of first infusion + 1).

The exposure to study drug is defined as the cumulative number of injections taken by subjects, since dose is based on subjects' LBM.

The extent of exposure and study drug exposure will be summarized descriptively in a table.

A listing will present subject data for first dose date, last dose date, extent of exposure, and study drug exposure.

7.2.2. Treatment Compliance and Modifications

Treatment compliance is defined as

$$\text{Compliance (\%)} = \frac{(\text{Number of injections received}) \times 100}{\text{Number of injections planned to be received during the study}}$$

The overall study drug compliance rate will be summarized by treatment group using the descriptive statistics. The number and percentage of subjects in each of the following compliance rate categories (<80, >=80 to 100) will also be reported.

Percentages will be calculated out of the number of subjects who were dosed at that dosing period. The number and percentage of subjects in each compliance rate category will be presented.

8. Efficacy Analysis

All efficacy analyses will be performed using the FAS population. Specific analyses, detailed below, will be performed on the MITT and the PP populations.

8.1. Primary Efficacy Endpoint

HVPG will be collected at screening and 14 to 28 days after final dose (53-55 weeks), and used as a measure of portal hypertension. Both wedged hepatic venous pressure (WHVP) and free hepatic venous pressure (FHVP) will be measured for subjects without varices or with small varices. HVPG is defined as the difference between the WHVP and the FHVP. A single experienced investigator, [name] (Yale University), will evaluate all HVPG tracings at a central reading facility.

The HVPG will be summarized for the FAS population by visit and treatment group, for all scheduled visits, along with the change from baseline descriptively in a summary table and graphically. In addition, the number and percentage of subjects will be summarized by the following HVPG categories (mild portal hypertension (MPH) ie ≥ 6 mmHg to < 10 mmHg and clinically significant portal hypertension (CSPH) ie ≥ 10 mmHg).

8.1.1. Primary Analysis

The primary efficacy endpoint, change from baseline in HVPG at 1 year (53 to 55 weeks), will be analyzed using analysis of covariance (ANCOVA) with baseline values taken as a covariate using the FAS population at a significant level of 0.05 (2-sided). Treatment effect will be evaluated as a contrast of each active treatment versus placebo and described using continuous summary. To control the type I error rate due to multiple comparisons, the Bonferoni-Holm (1988) procedure for the comparison between treatment group and control will be implemented. Estimate of mean difference along with 95% CI will also be presented.

Missing HVPG at 1 year will be imputed using the last observation carried forward (LOCF) method. The sensitivity analysis will be performed on the change from baseline in HVPG based on the LOCF values in the FAS population using the same statistical methodology described above.

Additional sensitivity analyses for HVPG will include:

- Change from baseline in HVPG at 1 year in the MITT population.
- Change from baseline in HVPG at 1 year in the PP population.

The following subgroup analysis will also be conducted in the MITT population:

- Change from baseline in HVPG at 1 year by baseline HVPG category of MPH and CSPH
- Change from baseline in HVPG at 1 year by gender.
- Percentage of subjects who have $\geq 10\%$ and $\geq 20\%$ decrease at 1 Year in HVPG by baseline HVPG category of MPH and CSPH
- Percentage of subjects with HVPG at CSPH level at Baseline and at MPH level at 1 Year

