## 7.6 Sample Size Calculations

A total of approximately 156 subjects will be enrolled in the study. Sample size calculations are based on the comparison of the primary efficacy variable, change in HVPG from baseline, with the following assumptions (key assumptions discussed as follows):

1. True mean change in HVPG from baseline at 52 weeks in the placebo group,  $\Delta p = 0$
2. True mean change in HVPG from baseline at 52 weeks in either GR-MD-02 dose group,  $\Delta G = -2$  mm Hg
3. Common SD for difference in HVPG,  $\sigma = 3$  mm Hg
4. Null hypothesis,  $H_0: \theta = G - \Delta p = 0$
5. Type I error,  $\alpha = 0.05$  (2-sided significance test)
6. Power = 80%
7. Statistical test = 2-sample  $t$ -test for mean difference
8. Randomization ratio = 1:1:1
9. Drop-out rate of 25%

For a mean difference of 2 mm Hg and accounting for a 25% dropout rate, the total sample size of 156 subjects ( $n = 52$  subjects per group) will be required to achieve power of 80% with a 2-sided type I error rate of 0.05.

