## Discussion of assumptions:

1. True mean change in HVPG from baseline at 52 weeks in the placebo group was set at 0 mm Hg. While one might assume that the fibrosis would progress over a 1-year period and there might be a resultant increase in HVPG, the conservative assumption was made that there would be no change.
2. True mean change in HVPG from baseline at 52 weeks in either GR-MD-02 dose group was set at 2 mm Hg. A reduction of 2 mm Hg in HVPG was chosen because a change of this degree is likely to be of clinical significance. The results of pharmacological therapies, such as nonselective  $\beta$ -blockers have been remarkably consistent across therapeutic studies. If the HVPG is reduced by at least 20% from baseline, the risk of variceal bleeding, rebleeding, and other complications of portal hypertension such as ascites, spontaneous bacterial peritonitis and hepatorenal syndrome markedly decreases and survival improves (VillanuevaVillanueva 2009; Escorsell 2000; Abraldes 2003). In addition, a 10% reduction in HVPG has been shown to prevent the development of varices (Groszmann 2005). Therefore, it appears that a reduction in HVPG between 10% to 20% confers clinical benefit of reduced variceal bleeding. It is anticipated that the mean HVPG for the experimental groups will be between 10 mm Hg and 15 mm Hg, as in other similarly designed studies (Groszmann 2005). Therefore, a 2 mm Hg change in HVPG between placebo and treated groups would be between 15% and 20%, which is likely to be of clinical significance.
3. The common SD for difference in HVPG over 1 year for subjects in the placebo group was set at  $\sigma = 3$  mm Hg. This assumption was determined from primary data, obtained from the investigator ([name]), from a longitudinal clinical study (Groszmann 2005). Table 7-1 and Table 7-2 show data for subjects in the placebo group who had baseline and 12-month HVPG measurements ( $n = 82$ ), of which 32 subjects had a baseline HVPG  $<10$  mm Hg and 50 subjects had a baseline HVPG  $\geq 10$  mm Hg. From these data, the SD of the absolute change at 12 months in the placebo group was 2.85 mm Hg. Therefore, the assumption of 3 mm Hg for the sample size calculation appears valid.

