3.1. Overall Study Design and Plan

This is a Phase 2, multi-center, parallel group, North American, randomized, placebo-controlled, double-blind study of subjects with portal hypertension due to cirrhosis.

Approximately 156 subjects with portal hypertension (HVPG ≥ 6 mm Hg) will be enrolled in the study at 45 to 60 study centers in the US and Canada. The subject must have a liver biopsy showing cirrhosis (Ishak stage 5 or 6) presumably due to NASH, excluding subjects with medium and large varices and those with decompensated cirrhosis (as defined by the presence of clinically detectable ascites, any episode of variceal bleeding, and overt hepatic encephalopathy).

Subjects with portal hypertension and the appropriate biopsy findings will be randomized in a 1:1:1 ratio according to the randomization schedule to receive 1 of 3 treatment assignments: placebo, GR-MD-02 in dose of 2 mg/kg lean body mass (LBM), or GR-MD-02 in a dose of 8 mg/kg LBM administered every other week over a 52 week period for a total of 26 infusions. (Figure 3-1)

The study includes Prescreening, Screening, Treatment, Follow-up phases.

Prescreening: Prescreening may begin at Week -9 to evaluate the eligibility for diagnosis of NASH and FibroScan[®] (at sites where it is available). Subjects with qualifying diagnosis and FibroScan[®] score may proceed to screening.

Screening: The screening window is up to 8 weeks after prescreening visit. Subjects will undergo the following required procedures to assess eligibility during the screening period: EGD, HVPG measurement, liver biopsy, MBT (if available) and serum transaminases. Subjects who meet all of the inclusion criteria and none of the exclusion criteria will proceed to randomization and the treatment phase.

Treatment Phase: Subjects will be randomly assigned (1:1:1) to receive 1 of 3 treatment assignments before the first infusion and will be administered every other week over a 52 week period for a total of 26 infusions. Safety and efficacy assessment will be monitored during the treatment phase.

Medical Care of Cirrhosis During the Study: General care of subjects with cirrhosis will be maintained during the study, including screening for hepatocellular carcinoma, at the discretion of the investigator.

[figure not shown]
Post Final Visit (14-28 Days): All subjects will attend a visit (or visits) 14 to 28 days after final dose. During this visit, selected safety and efficacy assessments will be collected/performed.

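### The CSPH-to-MPH summary at 1 year omits subjects who fall below 6 mm Hg, so it understates the arm difference if the drug lowers HVPG

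*SAP*

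**What the plan says.** SAP 8.1 (Primary Efficacy Endpoint) states that "the number and percentage of subjects will be summarized by the following HVPG categories", and names two: "mild portal hypertension (MPH) ie ≥ 6 mmHg to < 10 mmHg" and "clinically significant portal hypertension (CSPH) ie ≥ 10 mmHg". No class lies below 6 mm Hg. The SAP addendum repeats the MPH limits as 6 to below 10 and adds no lower class.

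The limits match the entry rule in SAP 3.1: "Approximately 156 subjects with portal hypertension (HVPG ≥ 6 mm Hg) will be enrolled". Every baseline value therefore falls into one class or the other.

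SAP 8.1.1 (Primary Analysis) then lists, among the MITT subgroup analyses, "Percentage of subjects with HVPG at CSPH level at Baseline and at MPH level at 1 Year". It names no test and no denominator. The bullet just above it reports the percentage of subjects with at least a 10% and at least a 20% "decrease at 1 Year in HVPG by baseline HVPG category of MPH and CSPH".

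**The concern.** A classification that is complete at baseline is reused as an outcome at 1 year, where it is not complete. A CSPH subject who ends at 9 mm Hg reaches the MPH class. One who ends at 5 mm Hg is in neither class and, on the stated limits, is not counted. For a given baseline, the subjects left out have improved more than those counted.

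The two adjacent bullets would disagree about the same person. A fall from 11 to 5 is 6/11 = 55%, which meets both the 10% and the 20% criterion, yet that subject is missing from the CSPH-to-MPH percentage.

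If the drug works, the omission falls more heavily on the active arms and the summary understates the difference. The missing denominator (baseline-CSPH subjects, or all MITT subjects) leaves a second choice that could be made after unblinding.

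**Working it through.** **Direction.** Among baseline-CSPH subjects, P(6 to <10) = P(<10) − P(<6). Taking active minus placebo:

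difference as worded = difference in P(<10) − difference in P(<6).

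A downward shift on active makes the last term positive, so the worded difference is too small. With no shift the term is zero.

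**Do values below 6 occur?** In Protocol Table 7-1 the placebo group of the cited timolol study has a baseline minimum of 6 and a 12-month minimum of 4. The table does not give the baseline of the subject who reached 4.

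**Inputs.**
- Effect 2 mm Hg, SD of change 3, dropout 25%, 52 per arm (Protocol 7.6, SAP 4.1). These reproduce the plan's sample size closely: a two-sample t-test at two-sided 0.05 and 80% power needs 37 per arm, and 37/0.75 rounds up to 50, against 52 stated.
- Zero placebo change (Protocol 7.6, assumption 1: "True mean change in HVPG from baseline at 52 weeks in the placebo group").
- Baseline mean 11.29, SD 3.97, quartiles 8, 10.75 and 14, range 6 to 23.5; 12-month SD 3.82; SD of change 2.85 (Tables 7-1 and 7-2).
- CSPH share: the protocol reports 82 placebo subjects, "of which 32 subjects had a baseline HVPG" below 10, so 50/82 = 61% are CSPH.

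The plan gives no figure for this summary, so its size has to be modelled.

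**One baseline value, by hand.** Baseline 11, SD of change 3, no regression to the mean:
- Placebo: P(<6) = Φ(−5/3) = 4.8%; P(<10) = Φ(−1/3) = 36.9%.
- Active, shifted by −2: P(<6) = Φ(−1) = 15.9%; P(<10) = Φ(1/3) = 63.1%.
- Difference in P(<10) is 26.1 points and in P(<6) is 11.1 points, so the difference as worded is 15.0 points.

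The effect fades with higher baselines. P(<6), placebo v active, is 9% v 25% at baseline 10, 2% v 9% at 12, and 0.4% v 2% at 14.

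**Whole CSPH group, by simulation (4 million draws).** Baselines were drawn to match the quartiles, range and 32/82 share above. For regression to the mean, r = (3.97² + 3.82² − 2.85²)/(2 × 3.97 × 3.82) = 0.733, slope = 0.733 × 3.82/3.97 = 0.705, and residual SD = 3.82 × √(1 − 0.733²) = 2.60. The active arm is the placebo distribution shifted by −2 mm Hg.

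| Change model | Loss (points) | Share of the difference lost |
|---|---|---|
| Regression to the mean, residual SD 2.60 | 4.6 | 21% |
| Same slope, change SD raised to 3 | 5.2 | 25% |
| Independent of baseline, SD 2.85 | 5.1 | 28% |
| Independent of baseline, SD 3 | 5.5 | 31% |

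Ranges over the four models, as percentages of baseline-CSPH subjects:

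| 1-year HVPG | Active | Placebo | Difference (points) |
|---|---|---|---|
| Below 10 | 36.7-40.4% | 18.5-19.6% | 17.7-21.6 |
| 6 to <10 (as worded) | 29.2-34.3% | 16.7-18.0% | 12.2-17.0 |
| Below 6 (omitted) | 5.8-7.7% | 1.2-2.2% | 4.6-5.5 |

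**Sensitivity.** Four other baseline shapes (truncated normal, truncated lognormal, 6 + gamma, 6 + lognormal) widen the loss to 3.8-6.3 points, or 18-34% of the difference. At a 1 mm Hg effect the loss is 1.6-2.1 points (16-25%); at zero effect it is 0.

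**In subjects.** 61% of 52 is about 32 CSPH subjects per arm; 61% of 52 × 0.75 = 39 is about 24. Omitted on active: 5.8% × 24 = 1.4 to 7.7% × 32 = 2.5. Omitted on placebo: 1.2% × 24 = 0.3 to 2.2% × 32 = 0.7.

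**Against sampling error.** With about 38.5% v 19% below 10, the SE of the difference is √[(0.385 × 0.615 + 0.19 × 0.81)/n]: 11 points at n = 32 and 13 points at n = 24. The loss is at most 5.5/11 = 0.50 SE in the main range, and 6.3/11 = 0.57 SE at the widest.

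**If the denominator is all MITT subjects:** 0.61 × 4.6 = 2.8 to 0.61 × 5.5 = 3.4 points.

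**The case against.** The strongest reply is that the SAP never calls this bullet a responder rate. As a count of moves between two named classes it is accurate, and it understates something only if the quantity of interest is HVPG below 10. A programmer might also class a value below 6 as improved, so exclusion is the literal reading rather than a certain outcome. Both points are fair, but neither removes the problem. A count of CSPH subjects who improve, leaving out those who improve most, is unlikely to be what was intended, and a SAP should not leave the choice to programming.

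Other summaries do capture these subjects: the 10% and 20% decreases, the change by baseline category, and the by-visit HVPG summary. That stands, and it limits the importance of the point.

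The documents show no CSPH subject falling below 6, because the baseline behind the 12-month minimum of 4 is unknown. That also stands: the frequency is modelled and rests on another trial's placebo group.

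Missing data could shrink the loss. HVPG is measured only at screening and at weeks 53-55, so LOCF would usually carry the baseline forward, and MITT membership does not require a 1-year HVPG. If LOCF applied to this bullet, which the SAP does not say, and 25% were missing, the loss would be 0.75 × 4.6 = 3.5 to 0.75 × 5.5 = 4.1 points. The proportion of the difference lost would not change.

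**Conclusion.** The concern holds. Applied as written, the class limits exclude CSPH subjects who end below 6 mm Hg, and a true HVPG reduction makes the summary understate the arm difference. The direction follows from the definitions, given a downward shift in the active arm.

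The size depends on the assumed baseline shape, a uniform shift and zero placebo change. At the planned 2 mm Hg effect it is about 4 to 6 points, roughly a fifth to a third of the difference, and somewhat fewer points if LOCF applies. That is one to three active subjects per arm and about half a standard error or less, slightly more at the extreme of the shapes tried.

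Materiality is low. The item is an untested MITT summary outside the gatekeeping order. The primary ANCOVA, the change by baseline category and the 10% and 20% decrease summaries are unaffected. The addendum subgroups are defined on baseline HVPG, where the two classes are complete, and are not in error.

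**What to change.** In SAP 8.1.1, define the event as baseline HVPG of 10 mm Hg or more and 1-year HVPG below 10 mm Hg, and state that the denominator is MITT subjects with CSPH at baseline. In SAP 8.1, if the HVPG category table is produced after baseline, add a row for values below 6 mm Hg.

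The cost is one line in each section. No new data are needed, and neither alpha nor the primary analysis changes.
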